#### **5.6. Safety Analyses**

The safety analyses will be descriptive in nature and will include the following:

- Exposure to IP
- AEs
- Laboratory data
- Vital signs
- ECG
- Physical examination
- Neurological examination
- C-SSRS
- Exposure to COVID-19

All safety analyses for the RCP and OLE Period will be conducted based on the Safety Set (SS) and OLE Set.

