### 5.6.3. Laboratory Tests

The analysis of central laboratory parameters (hematology, clinical chemistry, and urinalysis) will be summarized descriptively. Laboratory results based upon standardized units will be used for analyses. The last record will be used if there are multiple records of laboratory measurements at Baseline or post-Baseline Visits. The following analyses will be performed:

- Actual laboratory results, baseline values, and changes from Baseline will be summarized using descriptive statistics (mean, SD, etc.) for each scheduled study visit and for the last visit within each period for the respective laboratory parameter.
- Shift analyses will be conducted by calculating the number and percentage of participants in the low, normal, and high category combinations at both Baseline and post-Baseline Visits; the total number of participants with nonmissing values at both Baseline and post-Baseline Visits will be used as the denominator for the percentage calculation.
- The number (%) of participants meeting the criteria in [Table 7](#) for the liver function-related laboratory values (alanine aminotransferase [ALT], aspartate aminotransferase [AST], alkaline phosphatase [ALP], and total bilirubin [TBL]) will be provided.

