**Table 7: Abnormality Criteria for Liver Function Laboratory Values and Analysis Timepoints**

Criteria	Analysis Timepoints
ALT 
 
• <math>> 3 \times \text{ULN}</math>
 
• <math>> 5 \times \text{ULN}</math>
 
• <math>> 10 \times \text{ULN}</math>
 
• <math>> 20 \times \text{ULN}</math>
 
	
 
• By scheduled visit
 
• Any post-Baseline value
 

AST 
 
• <math>> 3 \times \text{ULN}</math>
 
• <math>> 5 \times \text{ULN}</math>
 
• <math>> 10 \times \text{ULN}</math>
 
• <math>> 20 \times \text{ULN}</math>
 
	
 
• By scheduled visit
 
• Any post-Baseline value
 

$\text{ALT} > 3 \times \text{ULN}$ and $\text{TBL} > 2 \times \text{ULN}$	
 
• By scheduled visit
 

$\text{ALT} > 3 \times \text{ULN}$ and $\text{ALP} < 2 \times \text{ULN}$ and $\text{TBL} \geq 2 \times \text{ULN}$	
 
• By scheduled visit
 

Criteria involving multiple laboratory analytes should be evaluated concurrently, ie, based on the same sample.

For any post-Baseline value, a participant can contribute to multiple categories.

Abbreviations: ALP = alkaline phosphatase; ALT = alanine aminotransferase; AST = aspartate aminotransferase; TBL = total bilirubin; ULN = upper limit of normal

[Table 8](#) provides an overview of the laboratory data analyses for different periods, underlying analysis sets, treatment group display convention, the definition of baseline values, and laboratory data analyses. An “X” in the table represents that an analysis will be performed for the period.

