#### **5.7.5.2. Subgroup Analyses for Laboratory Data**

The abnormality criteria for liver function laboratory values (Table 7) will be summarized for the following subgroups; no p-value will be produced for these subgroup analyses:

- Stable use of riluzole at baseline (yes, no)
- Stable use of edaravone at baseline (yes, no)

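### The two combined liver criteria in SAP Table 7 leave out AST and use different bilirubin cuts, so an AST-led rise with raised bilirubin gets no joint count and the two rows are not nested

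*SAP*

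**What the plan says.** SAP section 5.6.3 introduces the liver summary as a count of participants meeting the Table 7 criteria, for "liver function-related laboratory values (alanine aminotransferase [ALT], aspartate aminotransferase [AST], alkaline phosphatase [ALP], and total bilirubin [TBL]) will be provided". As printed, Table 7 contains:

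| Row | Transaminase | ALP | Total bilirubin |
|---|---|---|---|
| ALT alone | ALT > 3, 5, 10, 20 x ULN | none | none |
| AST alone | AST > 3, 5, 10, 20 x ULN | none | none |
| Combined A | ALT > 3 x ULN | none | > 2 x ULN |
| Combined B | ALT > 3 x ULN | < 2 x ULN | >= 2 x ULN |

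The table's note on the combined rows reads: "Criteria involving multiple laboratory analytes should be evaluated concurrently, ie, based on the same sample".

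SAP section 5.7.5.2 then reuses the table by stable riluzole and stable edaravone use: "The abnormality criteria for liver function laboratory values (Table 7) will be summarized for the following subgroups". On the status of all this, SAP section 5.6 says: "The safety analyses will be descriptive in nature and will include the following".

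**The concern.** Table 7 treats the two transaminases as equals when they stand alone, then drops one of them when bilirubin is added, without giving a reason. The combined rows are the only planned tabulation of transaminase and bilirubin elevation in the same sample, both overall and in the two background-therapy subgroups. A reader who wants to know whether anyone had both will look there, and AST-led cases with ALT at or below 3 x ULN will not be in the count.

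The second problem is internal consistency. Row B adds an ALP condition to row A, so one expects everyone in B to be in A as well. Because B accepts bilirubin equal to 2 x ULN and A does not, that expectation can fail, and a table that shows it failing would look like a programming error.

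The trial stopped for futility, so safety description is a large part of what remains to be reported. That makes a clean case definition worth having, even though no test depends on it.

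**Working it through.** The documents state no power, event count or error rate for this table, so there is no figure of the plan to reproduce. The check is of the threshold logic, followed by one illustration of size.

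**Inputs.** The four rows above and the same-sample rule (SAP Table 7); the planned total of 354 and the 2:1 ratio (SAP section 3).

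**1. AST-led samples.** Both combined rows require ALT > 3 x ULN. If ALT <= 3 x ULN, neither can be met, whatever AST, ALP and bilirubin are. Take AST 4, ALT 2.5 and TBL 2.5 x ULN in one sample:

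- AST alone, > 3: met.
- Combined A: ALT 2.5 > 3 is false, so not met.
- Combined B: same reason, not met.

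With the transaminase term changed to ALT or AST > 3 x ULN, A is met (4 > 3 and 2.5 > 2), and B is met if ALP < 2 x ULN. A sample in which AST exceeds ALT but ALT is also above 3 x ULN is already counted as written. The gap is confined to ALT <= 3 x ULN.

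**2. What else would show such a sample.** Table 7 has no bilirubin-only row. The shift analysis in section 5.6.3 and the abnormal-value summary in Table 8 would register the bilirubin as high, but parameter by parameter, against the normal range and not as a multiple of ULN. The Table 8 box plots cover ALT and AST but not bilirubin or ALP. Section 5.1 provides by-patient listings. The data are visible; the joint count is not tabulated.

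**3. Nesting of the two rows.** A sample is in B but not in A only if ALT > 3, ALP < 2, TBL >= 2 and not TBL > 2, which means TBL exactly 2.0 x ULN. Example: ALT 4, TBL 2.0, ALP 1.0 x ULN.

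- As written: A = 0, B = 1.
- Both cuts at > 2: A = 0, B = 0.
- Both cuts at >= 2: A = 1, B = 1.

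Under either common cut, B is A plus one further condition, so B can never exceed A.

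For the total in B to exceed the total in A as written, samples at exactly 2.0 x ULN with ALP < 2 must outnumber those with TBL > 2 and ALP >= 2 (all with ALT > 3). For instance, two samples like the one above plus one with ALT 5, TBL 3, ALP 2.5 x ULN give A = 1 and B = 2.

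**4. Size, under an assumption.** Assume the ravulizumab safety denominator equals the plan: 354 x 2/3 = 236. The two-sided exact 95% upper limits are:

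- 0 of 236: 1 - 0.025^(1/236) = 0.0155, so 0% with upper limit 1.6%.
- 1 of 236: 1/236 = 0.0042, so 0.4%; the upper limit is the 97.5% quantile of Beta(2, 235) = 0.0234, so 2.3%.

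**The case against.** The strongest reply is that the plan breaks no promise. Section 5.6.3 names four analytes and all four appear somewhere in Table 7. Nothing says the joint rule will use either transaminase. AST can come from muscle, and this is a population with progressive weakness and atrophy, so an ALT-only joint rule is a defensible choice for specificity. That stands as a possible reason. The SAP does not state it, however, and requiring raised bilirubin in the same sample already screens out most isolated muscle-derived AST.

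A reader might infer that an AST-led case would be reported as absent, or that a zero in a combined row would be false. The documents do not support that. The AST rise is counted in the AST row, both by scheduled visit and for any post-baseline value. The bilirubin enters the shift and abnormal-value summaries and the listings. Under Protocol section 8.3.8 a change the investigator considers clinically relevant is also recorded as an adverse event. A zero in a row labelled ALT plus bilirubin is correct for that label.

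It is also fair to say that the bilirubin mismatch bites only at exactly 2.0 x ULN, that the SAP never calls one row a subset of the other, and that the analysis is descriptive in a study already stopped for futility, so no p-value or conclusion depends on it. All of this limits the weight of the point. It does not remove the missing joint count or the unexplained difference between the two cuts.

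**Conclusion.** The point holds as a modest specification gap. Table 7 provides no joint count for samples with AST > 3, ALT <= 3 and bilirubin > 2 x ULN, and its two combined rows are not nested because their bilirubin inequalities differ. Both follow from the printed criteria without any assumption.

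The practical size cannot be derived from the documents: they give no event counts, no actual Safety Set size, and no laboratory rounding rules that would show how often a value falls exactly on 2.0 x ULN. On the assumed denominator of 236, one additional joint case is a change of 0.4 percentage points in a descriptive rate. The actual denominator may differ from the plan.

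The stronger claims, that cases vanish from the report or that the narrower row will exceed the broader one, should not be made. The first is contradicted by the other planned summaries. The second is possible but needs an unlikely run of boundary values. Efficacy, type I error and power are not touched. Whether unscheduled samples count towards the combined rows is a separate matter.

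**What to change.** In SAP Table 7:

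- Replace the ALT term in both combined rows by ALT or AST > 3 x ULN. The ALT-only count may be kept alongside for readers who prefer it.
- Use one bilirubin inequality, either > 2 or >= 2 x ULN, in both combined rows.
- Keep the same-sample rule.
- Carry the revised rows into the riluzole and edaravone subgroup tables of section 5.7.5.2.

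If the sponsor prefers ALT only, a sentence giving the reason would settle that half of the point; the bilirubin cut should be aligned in any case.

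The cost is an edit to two table rows and a small programming change. ALT, AST, ALP and total bilirubin are already in the protocol's required laboratory panel (Protocol Table 9), so no new data are needed. The downside is an occasional flag from muscle-derived AST, limited by the bilirubin condition.

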**Table 7: Abnormality Criteria for Liver Function Laboratory Values and Analysis Timepoints**

Criteria	Analysis Timepoints
ALT 
 
• <math>> 3 \times \text{ULN}</math>
 
• <math>> 5 \times \text{ULN}</math>
 
• <math>> 10 \times \text{ULN}</math>
 
• <math>> 20 \times \text{ULN}</math>
 
	
 
• By scheduled visit
 
• Any post-Baseline value
 

AST 
 
• <math>> 3 \times \text{ULN}</math>
 
• <math>> 5 \times \text{ULN}</math>
 
• <math>> 10 \times \text{ULN}</math>
 
• <math>> 20 \times \text{ULN}</math>
 
	
 
• By scheduled visit
 
• Any post-Baseline value
 

$\text{ALT} > 3 \times \text{ULN}$ and $\text{TBL} > 2 \times \text{ULN}$	
 
• By scheduled visit
 

$\text{ALT} > 3 \times \text{ULN}$ and $\text{ALP} < 2 \times \text{ULN}$ and $\text{TBL} \geq 2 \times \text{ULN}$	
 
• By scheduled visit
 

Criteria involving multiple laboratory analytes should be evaluated concurrently, ie, based on the same sample.

For any post-Baseline value, a participant can contribute to multiple categories.

Abbreviations: ALP = alkaline phosphatase; ALT = alanine aminotransferase; AST = aspartate aminotransferase; TBL = total bilirubin; ULN = upper limit of normal

[Table 8](#) provides an overview of the laboratory data analyses for different periods, underlying analysis sets, treatment group display convention, the definition of baseline values, and laboratory data analyses. An “X” in the table represents that an analysis will be performed for the period.

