**Table 8: Overview of Analysis of Laboratory Data for RCP (SS)**

Type of Analysis	Assessment Performed	Additional Notes
Actual value and change from Baseline	X	
Abnormal laboratory values (with respect to normal range)	X	
Shift analysis of abnormality compared to Baseline	X	
Liver function abnormality	X	
Box plots	X	ALT, AST, creatinine, glucose, hematocrit, hemoglobin, lymphocytes neutrophils, leukocytes, and platelets

The treatment group display convention is “Ravulizumab, Placebo”, and the definition of baseline values is “Last nonmissing value prior to first RCP study drug infusion.”

Abbreviations: ALT = alanine aminotransferase; AST = aspartate aminotransferase; RCP = Randomized Controlled Period; SS = Safety Set

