**6.2.9. Analysis Windows**

Since the actual study visits for a participant may not exactly coincide with their targeted visit date, the actual visit date will be mapped to the analysis visits as described below.

The analysis visits for the RCP will be derived using prespecified windows around the number of days during the study since the first dose of the study drug (called Day 1). The lower and the upper limits of the analysis windows are described in [Table 23](#).

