**6.2.9.1. Rules for Selecting the Analysis Records**

Only 1 record per analysis window will be selected for analysis. The following defines the selection rule.

1. Only scheduled visits of the specific endpoint will be selected and summarized in the tables and figures. If the earlier versions of the protocol and the final version of the protocol have different assessment schedules, then both scheduled visits will be used for the descriptive summary, as appropriate. Only the scheduled visits in the latest protocol will be selected for inferential analysis.
  - a. For example, an unscheduled SVC assessment may fall into the Week 22 analysis window. However, because Week 22 is not a scheduled visit for SVC, this record will not be flagged for descriptive and inferential analysis.
2. If there are multiple non-missing records within the same analysis window, the record closest to the target day will be selected.
3. If there are records with equal distance from the target day, the later record will be selected.
4. For CAFS analysis, only the last nonmissing record of ALSFRS-R will be selected.

Similar visit windows will be implemented for the OLE Period.

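### SAP Table 7 counts the two combined ALT/bilirubin criteria by scheduled visit only, so the SAP plans no count of participants who ever met them

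*SAP*

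**What the plan says.** SAP 5.6.3 plans the number and percentage of participants meeting the liver criteria in Table 7. The ALT and AST threshold rows have two analysis timepoints: each scheduled visit, and any post-baseline value. The two combined rows (ALT > 3 × ULN with TBL > 2 × ULN; ALT > 3 × ULN with ALP < 2 × ULN and TBL ≥ 2 × ULN) have the scheduled-visit timepoint and no other. The footnote reads "Criteria involving multiple laboratory analytes should be evaluated concurrently, ie, based on the same sample".

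Three further rules decide which samples reach a by-visit row:

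- SAP 6.2.9.1, rule 1: "Only scheduled visits of the specific endpoint will be selected and summarized in the tables and figures". Its worked example is an unscheduled SVC record in the Week 22 window: "because Week 22 is not a scheduled visit for SVC, this record will not be flagged for descriptive and inferential analysis".
- SAP 6.2.9.1, rule 2: "If there are multiple non-missing records within the same analysis window, the record closest to the target day will be selected".
- SAP 5.6.3, for laboratory data: "The last record will be used if there are multiple records of laboratory measurements at Baseline or post-Baseline Visits".

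Under SAP 6.2.9, "the actual visit date will be mapped to the analysis visits as described below", using the windows in Table 23. Protocol Table 1 schedules laboratory tests after Day 1 at Weeks 2, 10, 18, 26, 34, 42 and 50, or at early discontinuation (ED). It also allows extra visits. Protocol 10.2 allows extra tests at any time, and Protocol 8.3.8 asks for clinically significant abnormal results to be repeated. SAP 5.7.5.2 reuses the Table 7 criteria for subgroups defined by stable riluzole and edaravone use.

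**The concern.** The combined rows are the only planned by-arm count of ALT and bilirubin raised in the same sample. Table 7 has no row for bilirubin alone, and the other laboratory summaries do not link analytes within a sample. If these rows see only scheduled visits, two things follow. A participant whose only qualifying sample came from an unscheduled draw is missing from them. And even with no unscheduled draws, a set of visit-specific counts does not say how many different participants ever met the criterion.

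The SAP does otherwise elsewhere. ALT and AST alone have an any-post-baseline count, and the vital-sign criteria (SAP 5.6.4) and QT criteria (SAP 5.6.5) are counted once per participant over the randomized period. At stake is a complete participant count by arm, and by subgroup if the subgroup tables follow the same timepoints.

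**Working it through.** The plan states no figure to reproduce. The check sets the windows in SAP Table 23 against the laboratory schedule in Protocol Table 1 and then applies the selection rules to simple cases.

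**1. Windows with no scheduled laboratory test.** These are Week 6 (Days 30–57), Week 14 (Days 86–113) and Week 22 (Days 142–169). Each spans 28 days, so 3 × 28 = 84. From Day 2 to the Week 50 target day (Day 351) there are 350 days, and 84/350 = 24.0%. An unscheduled draw here is the laboratory equivalent of the SVC example in rule 1, so its exclusion is certain. In the other windows it depends on whether rule 1 is read as excluding every unscheduled record or only records in a window without a scheduled assessment.

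**2. Two records in one window.** Suppose the scheduled sample falls on its target day and a later ED sample falls in the same window. The closest-to-target rule then drops the ED sample. Days after target and within the window, for laboratory visits before Week 50:

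| Week 2 | Week 10 | Week 18 | Week 26 | Week 34 | Week 42 | Sum |
|---|---|---|---|---|---|---|
| 14 | 14 | 14 | 28 | 28 | 28 | 126 |

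From Day 2 to Day 350 there are 349 days, and 126/349 = 36.1%. Like the 24%, this is a share of calendar days, and it applies only under closest-to-target.

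**3. Cases.** Participants counted in the first combined row, with unscheduled draws excluded under rule 1 and ED samples mapped by day:

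| Samples | Last record | Closest to target | Any sample |
|---|---|---|---|
| Day 71 normal; Day 100 unscheduled, qualifying; Day 127 normal | 0 | 0 | 1 |
| Day 71 qualifying; Day 100 unscheduled, normal; Day 127 normal | 1 | 1 | 1 |
| Day 183 qualifying; ED Day 200 normal | 0 | 1 | 1 |
| Day 183 normal; ED Day 200 qualifying | 1 | 0 | 1 |
| ALT and TBL raised only in different samples | 0 | 0 | 0 |

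The first line is the main gap: neither rule counts the participant. Lines three and four show that the two rules can disagree, and the SAP does not say which governs. One way to reconcile them is to use the last record within a visit and the closest to target within a window; line four then still counts 0. The last line shows that any-sample counting keeps the same-sample requirement.

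**4. Non-additivity.** With by-visit counts alone, the number who ever met the criterion lies between the largest visit count and the sum of the visit counts. One case at each of the 7 laboratory visits gives 1 to 7 participants. The planned ravulizumab arm is 354 × 2/3 = 236, so the range is 1/236 = 0.4% to 7/236 = 3.0%. This pattern is illustrative, but the bound needs no particular reading of rule 1.

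**The case against.** The strongest reply is that little depends on this. SAP version 2 reports a trial stopped for futility, its safety analyses are descriptive, and no decision rule uses the combined rows. Cases remain visible: Protocol 8.3.8 sends clinically relevant laboratory changes to the AE record, AEs are tabulated by arm, and the data are listed. Every combined case also has ALT > 3 × ULN, so the any-post-baseline ALT row bounds the number from above in each arm. That limits the consequence, but neither that upper bound nor a set of listings is a by-arm count of the same-sample criterion. SAP Appendix 4 also records safety outputs added after the futility decision, so safety counts still matter to the report.

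Other objections stand in part:

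- Repeats under Protocol 8.3.8 follow a result already judged abnormal. If that sample qualified at a scheduled visit, it is already counted (second case above). The gap is confined to participants whose only qualifying sample is unscheduled or not selected.
- The laboratory-specific last-record rule may be meant to override the general closest-to-target rule, in which case the 36% falls away. The SAP does not say so.
- The any-post-baseline entry for ALT and AST would ordinarily override rule 1. Rule 1 makes no exception for it, so a strict reading would restrict those rows too.
- SAP 5.7.5.2 names the criteria but no timepoints, so carrying the restriction into the subgroups is an inference.
- Table layouts are in a separate data presentation plan that is not available here and might include an overall row.

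**Conclusion.** The concern holds. The combined rows carry one timepoint where the ALT and AST rows carry two, and no other passage in the two documents plans an ever-met count for the combined criteria. Exclusion of an unscheduled qualifying sample is certain in the Week 6, 14 and 22 windows (84 of 350 days) and depends on the reading of rule 1 elsewhere. Failure to give the number of participants who ever met the criterion is certain in either case.

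The 24% and 36% describe days, not risk. The 36% also assumes closest-to-target selection and a scheduled sample taken exactly on its target day. The documents give no rate of concurrent elevation, so the number of participants affected cannot be estimated and may be zero. The conflict between the two record rules is a minor accompanying point. This is a worthwhile, inexpensive correction to a safety table and does not threaten the trial's conclusions.

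**What to change.** 1. Add an any-post-baseline timepoint to both combined criteria in Table 7. Evaluate it sample by sample, keeping the same-sample requirement, on all post-baseline central laboratory samples in the randomized period, including repeat, unscheduled and ED samples.
2. State that the record-selection rules of SAP 5.6.3 and 6.2.9.1 do not apply to any any-post-baseline count in Table 7, including the existing ALT and AST rows.
3. Add one sentence saying whether last-record or closest-to-target governs by-visit laboratory summaries.

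The criteria and thresholds stay as written. The cost is two table rows, repeated in the riluzole and edaravone subgroup tables, and two sentences of SAP text. No new data are collected, and abnormality counts may come out slightly higher. Results available only from a local laboratory would still not be counted. SAP 5.6.3 is confined to central laboratory parameters ("The analysis of central laboratory parameters (hematology, clinical chemistry, and urinalysis) will be summarized descriptively"), and Protocol 10.2 asks for a central sample alongside any local sample that is required, which limits that residual gap.
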